Animal reproduction studies have not been conducted. Immunoglobulins are known to cross the placenta; therefore fetal exposure to pembrolizumab is expected. Based on the mechanism of action, pembrolizumab may cause fetal harm if administered during pregnancy; an alteration in the immune response or immune mediated disorders may develop following in utero exposure.

Women of reproductive potential should use highly effective contraception during therapy and for at least 4 months after treatment is complete.

Breast-Feeding Considerations

It is not known if pembrolizumab is excreted into breast milk. The manufacturer recommends that breast-feeding be discontinued during therapy and for 4 months following the final dose. Immunoglobulins are excreted in breast milk; therefore pembrolizumab may be expected to appear in breast milk.

Monitoring Parameters

PD-L1 expression status in patients with NSCLC; liver function tests (AST, ALT, and total bilirubin); renal function; thyroid function (at baseline, periodically during treatment and as clinically indicated); glucose; signs/symptoms of colitis, hypophysitis, thyroid disorders, pneumonitis, infusion reactions.

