2.7 Withdrawals

Subjects may discontinue study treatment or withdraw their consent to participate in the study at any time without prejudice. The investigator may withdraw a subject from study treatment or from the study if, in his or her clinical judgment, it is in the best interest of the subject or if the subject cannot comply with the protocol.

In addition, any of the following conditions require discontinuation of the subject from study treatment:

- An AE or intercurrent illness that in the opinion of the investigator warrants the subject's withdrawal from study treatment;
- The investigator believes it is not in the best interest of the subject to continue on study
- Specific conditions described in the Management of Adverse Events Sections 3.3.2 and 3.3.2.1;
- Necessity for treatment with other anticancer treatment prohibited by protocol;
- Sexually active subjects who refuse to use medically accepted barrier methods of contraception (eg, male condom, female condom) during the course of the study and for 4 months after discontinuation of study treatment;
- Women who become pregnant or are breastfeeding;
- If the subject does not recover from his or her toxicities to tolerable Grade ≤ 2 within 6 weeks, the subject will have study treatment discontinued unless there is unequivocal evidence that the subject is benefitting. In this situation, a subject may be able to restart therapy with a dose reduction upon resolution of the toxicity and with agreement of the principal investigator / Sponsor;
- Request by regulatory agencies for termination of treatment of an individual subject or all subjects under the protocol;
- Significant noncompliance with the protocol schedule in the opinion of the investigator;
- The minimum dose of study treatment will be 20 mg once daily (qd). Subjects who cannot tolerate 20 mg qd will have study treatment discontinued;

- Progressive disease (PD) or the subject no longer experiences clinical benefit as determined by the investigator

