3.4 Concomitant Medications and Therapies

3.4.1 Anticancer Therapy

Local intervention is discouraged unless medically unavoidable. Subjects receiving local intervention (eg, palliative radiation) are allowed to continue to receive study treatment at the investigator's discretion.

Pembrolizumab Drug information:

Brand Names: US

Keytruda

Dosing: Adult

Head and neck cancer, squamous cell, recurrent or metastatic:

IV: 200 mg once every 3 weeks until disease progression, unacceptable toxicity, or (in patients without disease progression) for up to 24 months.

Dosing: Geriatric

Refer to adult dosing.

Dosing: Renal Impairment

No dosage adjustment necessary. In a pharmacokinetic study, no difference in clearance was noted for patients with eGFR ≥ 15 mL/minute/1.73 m².

Dosing: Hepatic Impairment

Hepatic impairment prior to treatment initiation:

Mild impairment (total bilirubin \leq ULN and AST $>$ ULN or total bilirubin $>$ 1 to 1.5 times ULN and any AST): No dosage adjustment necessary.

Moderate (total bilirubin $>$ 1.5 to 3 times ULN and any AST) to severe (total bilirubin $>$ 3 times ULN and any AST) impairment: There are no dosage adjustments provided in the manufacturer's labeling (has not been studied).

Hepatotoxicity during treatment:

Note: For patients with baseline grade 2 ALT or AST abnormalities due to liver metastases, permanently discontinue if AST or ALT increases by $\geq 50\%$ (relative to baseline) and persists at least 1 week.

AST or ALT $>$ 3 to 5 times ULN or total bilirubin $>$ 1.5 to 3 times ULN: Withhold treatment; may resume therapy upon recovery to grade 0 or 1 toxicity. Also administer corticosteroids (prednisone 0.5 to 1 mg/kg/day [or equivalent] followed by a taper).

AST or ALT $>$ 5 times ULN or total bilirubin $>$ 3 times ULN: Permanently discontinue. Also administer corticosteroids (prednisone 1 to 2 mg/kg/day [or equivalent] followed a taper).

Ocular toxicity: Optic neuritis which could manifest as a sudden onset of vision loss, loss of color vision, pain when moving eyes, and/or loss of peripheral vision. It may affect one or both eyes at the same time (optic neuritis).

Dosing: Adjustment for Toxicity

Withhold treatment for any of the following (may resume upon recovery to grade 0 or 1 toxicity):

Colitis, moderate (grade 2) or severe (grade 3); also administer corticosteroids (prednisone 1 to 2 mg/kg/day [or equivalent] followed by a taper).

Endocrinopathies:

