3.4.4 Prohibited or Restricted Therapies

The following therapies are prohibited while the subject is on study:

- Any investigational agent or investigational medical device;
- Any drug or herbal product used specifically for the treatment of SCCHN;

- Therapeutic doses of oral anticoagulants (eg, warfarin or other coumarin-related agents, direct thrombin or direct FXa inhibitors, or antiplatelet agents such as clopidogrel, or chronic use of aspirin above low dose levels for cardioprotection per local applicable guidelines);
- Any other systemic anticancer treatment (eg, chemotherapy, immunotherapy, radionuclides) and local anticancer treatment such as surgery, ablation, or embolization.

The following therapies should be avoided if possible, while the subject is on study:

- Palliative external radiation to bone metastasis for bone pain should not be performed while on study. Subjects who have such an intervention may be considered not evaluable (and may be assigned a censoring or progression date) for certain efficacy endpoints;
- Erythropoietic stimulating agents (eg, epoetin alfa and darbepoetin alfa) should not be used based on a report of increased risk of tumor recurrence and/or progression associated with erythropoietin(101);
- Chronic co-administration of cabozantinib with strong inducers of the CYP3A4 family (eg, phenytoin, carbamazepine, rifampin, rifabutin, rifapentine, phenobarbital, and St. John's Wort) may significantly decrease cabozantinib concentrations and should be avoided. Selection of alternate concomitant medications with no or minimal CYP3A4 enzyme induction potential is recommended;
- Caution must be used when discontinuing treatment with a strong CYP3A4 inducer in a subject who has been concurrently receiving a stable dose of cabozantinib, because this could significantly increase the exposure to cabozantinib;
- Co-administration of cabozantinib with strong inhibitors of the CYP3A4 family (eg, ketoconazole, itraconazole, clarithromycin, indinavir, nefazodone, nelfinavir, and ritonavir) may increase cabozantinib concentrations and should be avoided. Grapefruit and Seville oranges may also increase plasma concentrations of cabozantinib and should be avoided.

Additional information on potential drug interactions with cabozantinib is provided in Section 3.4.5.

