Serum chemistry	
 • albumin • ALP • amylase • ALT • AST • bicarbonate • BUN • chloride • creatinine • GGT • Glucose • ionized calcium or total and corrected calcium • lactate dehydrogenase • lipase • magnesium • phosphorus • potassium • sodium • total bilirubin • total protein
Urinalysis	
 • appearance • color • pH • specific gravity • ketones • protein • UPCR • Glucose • bilirubin • nitrite • creatinine • urobilinogen • occult blood (microscopic examination of sediment will be performed only if the results of the urinalysis dipstick evaluation are positive)
Other	
 • TSH, Free T3 and T4 • Pregnancy test (urine or serum) for women of child-bearing potential • Blood for research studies • PT/INR or PTT • 24 hour urine collection for protein

ALP, alkaline phosphatase; ALT, alanine aminotransferase; AST, aspartate aminotransferase; BUN, blood urea nitrogen; ESR, erythrocyte sedimentation rate ; GGT, γ -glutamyltransferase; INR, International Normalized Ratio; PT, prothrombin time; PTT partial thromboplastin time; RBC, red blood cell; TSH, thyroid stimulating hormone; UPCR, urine protein/creatinine ratio; WBC, white blood cell.

Abnormalities in clinical laboratory tests that lead to a change in subject management (eg, dose delayed [withheld] or reduced, requirement for additional medication, treatment or monitoring)

are considered clinically significant for the purposes of this study, and will be recorded on the Adverse Events Case Report Form (CRF). If laboratory values constitute part of an event that meets criteria defining it as serious, the event (and associated laboratory values) must be reported as an SAE.

- **Tumor Assessment**

Response Criteria (RECIST 1.1)

For subjects who have measurable disease at baseline, this is a summary of overall response status calculation.

Evaluation of Target Lesions

Complete Response (CR): Disappearance of all target lesions

Partial Response (PR): At least a 30% decrease in the sum of the longest diameter (LD) of target lesions, taking as reference the baseline sum LD

Progressive Disease (PD): At least a 20% increase in the sum of the LD of target lesions, taking as reference the smallest sum of the LD recorded since the treatment started or the appearance of one or more new lesions

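### Sections 3.4.1, 3.4.4 and 2.7 conflict on continuing study treatment after surgery, ablation or embolization, and no response rule keeps a locally treated target lesion from counting toward ORR

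*Combined protocol and SAP*

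**What the plan says.** **Whether study treatment continues.** Section 3.4.1 (Anticancer Therapy) states that "Local intervention is discouraged unless medically unavoidable". It then provides that "Subjects receiving local intervention (eg, palliative radiation) are allowed to continue to receive study treatment" at the investigator's discretion. The term is general, and radiation is only its example. Section 3.4.4 (Prohibited or Restricted Therapies) puts "local anticancer treatment such as surgery, ablation, or embolization" on the list of therapies prohibited on study. Section 2.7 (Withdrawals) includes "Necessity for treatment with other anticancer treatment prohibited by protocol" among the conditions that require discontinuation of study treatment.

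**Radiation.** Section 3.4.4 handles this in a second, softer list, headed "The following therapies should be avoided if possible, while the subject is on study". The item there reads "Palliative external radiation to bone metastasis for bone pain should not be performed while on study", which is firmer than its own heading. Patients irradiated in this way "may be considered not evaluable (and may be assigned a censoring or progression date) for certain efficacy endpoints". External radiation to sites other than bone is named in neither list.

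**Response.** The primary endpoint (Section 2.1, Endpoints) is the proportion with CR or PR by RECIST v1.1. The Tumor Assessment part of Section 16 defines PR on target lesions as "At least a 30% decrease in the sum of the longest diameter (LD) of target lesions" relative to baseline, and CR as the disappearance of all of them. Section 18 (Sample Size) counts a patient as evaluable after treatment and one follow-up scan. None of the three mentions a lesion treated locally after baseline.

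**The concern.** There are two linked problems.

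First, a patient who has surgery, ablation or embolization may stay on study treatment under Section 3.4.1 but must come off under Sections 3.4.4 and 2.7. Two sites could handle the same case differently, each with text to support it.

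Second, whichever way that is settled, later scans can still enter the response assessment. A lesion removed or shrunk by local treatment lowers the sum of diameters just as a drug effect would. ORR is the primary endpoint of an open-label single-arm trial judged against a fixed count, so each response obtained this way moves the trial one step nearer to being called promising. The only efficacy provision, in Section 3.4.4, is optional, covers bone radiation alone and names no endpoint.

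**Working it through.** **1. The continuation rules side by side**

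| Intervention | 3.4.1 | 3.4.4 | 2.7 |
|---|---|---|---|
| Surgery, ablation, embolization | may continue, at discretion | prohibited | stop |
| Radiation to bone metastasis | may continue, at discretion | to be avoided if possible (item wording firmer) | not clearly triggered |
| Other external radiation | may continue, at discretion | not named | not clearly triggered |

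Only the first row is a clear contradiction.

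**2. When local treatment alone could give a PR**

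Let one target lesion make up a share *s* of the baseline sum and shrink by a fraction *f*, with the other lesions unchanged. The sum falls by *s* × *f*, so PR on target lesions needs *s* × *f* ≥ 0.30. A resected lesion (*f* = 1) suffices if *s* ≥ 0.30. A lesion that shrinks by 30% suffices only if it is the sole target lesion (*s* = 1). New lesions or unequivocal non-target progression would still make the patient PD.

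**3. Whether scans after local treatment can count**

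No text ends response assessment at local treatment. The paragraph accompanying Table 3-2 keeps response assessment, where available, for patients removed after interruptions of more than 6 weeks. Table 16-1 schedules a one-year scan for patients without prior progression. Procedures on study are foreseen: Section 3.3 gives surgical procedures as an example of a reason for interruption, and Section 3.3.2.7 covers stopping cabozantinib before major surgery.

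**4. The plan's own figures**

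Inputs from Section 18: n = 34; not promising if ≤ 9 responses, so success at ≥ 10; null ORR 0.15; alternative 0.35; stated type 1 error 0.05 and power 80%; reported single-agent ORR 18%; stop at 20 patients if ≤ 4 responses.

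- P(X ≥ 10 | 34, 0.35) = 0.804, which reproduces the stated 80%.
- P(X ≥ 10 | 34, 0.15) = 0.024, so the stated 0.05 holds as an upper bound.
- With the interim stop these become 0.771 and 0.021. The stated power therefore reproduces only without the interim.

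**5. Effect of credited responses**

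Suppose *k* patients count as responders only because of local treatment. They occupy *k* of the 34 places, so the other 34 − *k* must supply 10 − *k* responses:

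P(pass) = P(X ≥ 10 − *k*), X ~ Bin(34 − *k*, p)

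| *k* | Rise in observed ORR | p = 0.15 | p = 0.18 |
|---|---|---|---|
| 0 | – | 2.4% | 7.2% |
| 1 | 1/34 = 2.9 points | 5.0% | 12.5% |
| 2 | 2/34 = 5.9 points | 9.6% | 20.6% |

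**6. With the interim stop, *k* = 1**

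- Credited patient among the first 20: the other 19 need ≥ 4 responses at the look, and the other 33 need ≥ 9 overall. This gives 4.6% at 0.15 and 11.7% at 0.18.
- Credited patient among the last 14: the first 20 need ≥ 5, and the other 33 need ≥ 9 overall. This gives 4.1% and 10.6%.
- With no credited response: 2.1% and 6.4%.

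**7. The existing caveat**

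Dropping an irradiated non-responder also raises the observed rate. For example, 9/34 = 26.5% becomes 9/33 = 27.3%. It also conflicts with Section 18, under which one follow-up scan makes the patient evaluable.

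**The case against.** Much can be said for the plan. Local intervention is discouraged, entry requires inoperable disease, no more than one prior head-and-neck radiotherapy regimen is allowed, and progression ends treatment. Events may be few. The example in Section 3.4.1 is radiation, which Section 3.4.4 does not prohibit, so the two sections can largely be read together for radiation. The response text calls itself a summary, and the endpoint refers to RECIST v1.1 as a whole.

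Several stronger readings therefore fail:

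- A reader might infer that an irradiated patient must stop under Section 2.7. Radiation is not on the prohibited list, so that does not follow.
- A reader might infer that the rules credit local treatment to the drugs. They are silent; the defect is that they do not prevent it.
- A reader might infer that a neck mass shrinking by 30% is a PR. It is the sum of target diameters that must fall by 30%.
- A reader might lower the cutoff to 9 and keep n = 34, giving 5.9% at 15% and 14.4% at 18%. That lets the credited patient respond a second time. Corrected, one credited response stays just inside 0.05.

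What remains is the contradiction for surgery, ablation and embolization, and the absence of any analysis rule. Discouragement and inoperability lower the frequency but do not say how a scan is scored, and irradiation needs no operability. The documents reproduce no RECIST provision that would settle the matter.

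**Conclusion.** The point holds in two parts. For surgery, ablation and embolization, Section 3.4.1 contradicts Sections 3.4.4 and 2.7. For any local treatment of a target lesion, including radiation, the plan leaves open a route by which ORR could be raised.

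One credited response roughly doubles the chance of passing at a true ORR of 15%, from 2.4% to 5.0%, and uses up the stated 0.05. Two take it to 9.6%. With the interim stop, one gives 4.1% to 4.6%. At 18%, one credited response gives 12.5%, or 10.6% to 11.7% with the interim stop.

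These figures assume the number of credited responses, because the documents give no rate of local treatment, and they assume that the credited patients would not otherwise have responded. They show sensitivity. They do not show that ORR is inflated, and nothing in the documents supports that stronger statement or a claim that local treatment will be common.

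**What to change.** 1. Reconcile Section 3.4.1 with Sections 3.4.4 and 2.7 on surgery, ablation and embolization. In the same edit, make the radiation item in Section 3.4.4 agree with its heading and state the status of non-bone radiation. The direction is for the sponsor.
2. Add to Tumor Assessment in Section 16: best response for ORR is taken from scans before any local treatment of a target lesion and before any new systemic anticancer therapy; a patient without CR or PR by then stays in the denominator as a non-responder. State that, for ORR, this replaces the optional not-evaluable wording in Section 3.4.4.
3. Record the date and site of local treatment on the CRF. Section 3.4.2 requires concomitant medications but does not name radiation, surgery or ablation, so the documents do not show that these dates are already collected.

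**Cost.** This takes a few sentences and a CRF field. A true drug response first seen after local treatment is not counted. If one patient can never count, single-stage power at 35% becomes P(X ≥ 10 | 33, 0.35) = 77.0%, against 80.4%. For two patients it is P(X ≥ 10 | 32, 0.35) = 73.2%. Patients who respond before local treatment still count.

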3.4.2 Other Medications

All concomitant medications used by the subject (including prescription and over-the-counter medications, transfusions, vitamins, herbal remedies, and nutritional supplements) during the period from 28 days before the first dose of study treatment through 30 days after the date of the last dose of study treatment are to be recorded in the case report forms.

3.4.3 Allowed Therapies

- Antiemetics and antidiarrheal medications are allowed prophylactically in accordance to standard clinical practice if clinically indicated;
- Granulocyte colony-stimulating factors (G-CSF or GM-CSF) are allowed if used per clinical guidelines (eg, American Society of Clinical Oncology [ASCO] or [European Society for Medical Oncology] ESMO guidelines);
- Drugs used to control bone loss (eg, bisphosphonates and denosumab) are allowed if started before screening activities but may not be initiated or exchanged during the course of the study and require Sponsor approval;
- Transfusions, hormone replacement, and short term higher doses of corticosteroids should be utilized as indicated by standard clinical practice;

- Individualized anticoagulation therapy with heparin is allowed if it can be provided safely and effectively under the following circumstances:
 - *Low dose heparins for prophylactic use* are allowed if clinically indicated and the benefit outweighs the risk per the investigator's discretion.
 - *Therapeutic doses of low molecular weight heparins (LMWH) at the time of first dose* are allowed if the subject has no evidence of brain metastasis, has been on a stable dose of LMWH for at least 6 weeks, and has had no complications from a thromboembolic event or the anticoagulation regimen.
 - *Therapeutic doses of low molecular weight heparins (LMWH) after first dose* are allowed if clinically indicated (eg, for the treatment of deep venous thrombosis), and the benefit outweighs the risk per the investigator's discretion. For management of thromboembolic complications while on study, refer to Section 3.3.2.9.
 - Accepted clinical guidelines regarding appropriate management while receiving anticoagulation therapy with heparins must be followed. This includes, but is not limited to, subject education regarding potential adverse drug reactions, monitoring laboratory parameters, dose adjustments (eg, due to kidney dysfunction);
 - For restrictions on oral anticoagulants see Section 3.4.4.
- Administration of the PPI esomeprazole resulted in no clinically-relevant effect on cabozantinib plasma PK in healthy volunteers (Study XL184-018). Therefore, concomitant use of gastric pH modifying agents (ie, PPIs, H2 receptor antagonists, and antacids) is not contraindicated in subjects administered cabozantinib. Cimetidine should be avoided due to potential CYP interactions.

Potential drug interactions with cabozantinib are summarized in Section 3.4.5.

3.4.4 Prohibited or Restricted Therapies

The following therapies are prohibited while the subject is on study:

- Any investigational agent or investigational medical device;
- Any drug or herbal product used specifically for the treatment of SCCHN;

- Therapeutic doses of oral anticoagulants (eg, warfarin or other coumarin-related agents, direct thrombin or direct FXa inhibitors, or antiplatelet agents such as clopidogrel, or chronic use of aspirin above low dose levels for cardioprotection per local applicable guidelines);
- Any other systemic anticancer treatment (eg, chemotherapy, immunotherapy, radionuclides) and local anticancer treatment such as surgery, ablation, or embolization.

The following therapies should be avoided if possible, while the subject is on study:

- Palliative external radiation to bone metastasis for bone pain should not be performed while on study. Subjects who have such an intervention may be considered not evaluable (and may be assigned a censoring or progression date) for certain efficacy endpoints;
- Erythropoietic stimulating agents (eg, epoetin alfa and darbepoetin alfa) should not be used based on a report of increased risk of tumor recurrence and/or progression associated with erythropoietin(101);
- Chronic co-administration of cabozantinib with strong inducers of the CYP3A4 family (eg, phenytoin, carbamazepine, rifampin, rifabutin, rifapentine, phenobarbital, and St. John's Wort) may significantly decrease cabozantinib concentrations and should be avoided. Selection of alternate concomitant medications with no or minimal CYP3A4 enzyme induction potential is recommended;
- Caution must be used when discontinuing treatment with a strong CYP3A4 inducer in a subject who has been concurrently receiving a stable dose of cabozantinib, because this could significantly increase the exposure to cabozantinib;
- Co-administration of cabozantinib with strong inhibitors of the CYP3A4 family (eg, ketoconazole, itraconazole, clarithromycin, indinavir, nefazodone, nelfinavir, and ritonavir) may increase cabozantinib concentrations and should be avoided. Grapefruit and Seville oranges may also increase plasma concentrations of cabozantinib and should be avoided.

Additional information on potential drug interactions with cabozantinib is provided in Section 3.4.5.

